5. During treatment, if any drug-related and/or clinically significant toxicity occurs, retest frequently until stable or resolving and in accordance with GCP. **Note: CBC with differential and platelet count must be performed weekly during each cycle.**
6. To include BUN, phosphorus, magnesium, LDH, creatinine, uric acid, total protein, albumin, calcium, glucose, total bilirubin, ALP, AST, ALT, electrolytes (chloride, sodium, potassium, and bicarbonate), PT/INR (at screening only).
7. Lab urinalysis to include protein, specific gravity, glucose, and blood.
8. Tumor response must be monitored during treatment every 6 weeks \pm 5 days from Cycle 1-Day 1 regardless of dosing delays. The final assessment to be done 3 weeks following final ALDOXORUBICIN administration.
9. To include all medications taken within 30 days prior to study Randomization.
10. Subject will be followed until resolution of any drug-related AE or SAE occurring during the study, including within 30 days of last administration of study medication, or when the subject begins alternative therapy; whichever is sooner.
11. Cycle 4 and End of Treatment visit if later than Cycle 4. Additional testing can be done if clinically indicated.
12. Follow-up by telephone will be conducted in all subjects every 8 weeks to determine date of death.
13. If not done within last 14 days.
14. No need to repeat if performed within 21 days of Randomization.
15. ECGs will be performed pre-dose and at 1 hour post-dose (the anticipated maximal concentration).

CLINICAL PROTOCOL

TITLE: An Open-Label Pilot Phase 2 Study to Investigate the Preliminary Efficacy and Safety of Aldoxorubicin in Subjects with Unresectable Glioblastoma Whose Tumors Have Progressed Following Prior Treatment with Surgery, Radiation and Temozolomide

PROTOCOL NUMBER: ALDOXORUBICIN-P2-GBM-01

STUDY DRUG: Aldoxorubicin

IND NUMBER: 119437

SPONSOR: CytRx Corporation
[name]
[name]
[contact]
[contact]

SAFETY [contact]

SAFETY [contact]

ORIGINAL PROTOCOL: August 9, 2013

AMENDMENT 1: November 12, 2013

AMENDMENT 2: February 4, 2014

CONFIDENTIAL

The information contained in this document is confidential and the proprietary property of CytRx Corporation. Any unauthorized use or disclosure of such information without the prior written authorization of CytRx Corporation is prohibited.

SYNOPSIS

Name of Sponsor/Company: CytRx Corporation	
Protocol Number: ALDOXORUBICIN-P2-GBM-01	Phase of Development: 2

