Primary Objectives: The primary objective of this study is to determine the preliminary efficacy of administration of ALDOXORUBICIN to subjects with unresectable glioblastoma (GBM) whose tumors have progressed following prior treatment with surgery, radiation and temozolomide, as measured by PFS according to the Response Assessment in Neuro-Oncology (RANO) Working Group Criteria (see Appendix F) and OS.	
Secondary Objectives: The secondary objectives of this study are to evaluate the safety of ALDOXORUBICIN in this population assessed by the frequency and severity of adverse events (AEs), abnormal findings on physical examination, laboratory tests, vital signs, echocardiogram (ECHO) evaluations, electrocardiogram (ECG) results, weight, and the change in performance status as measured by the Karnofsky Performance Scale.	
Study Rationale and Significance: ALDOXORUBICIN is a novel prodrug that binds covalently to albumin in the circulation. The drug is accumulated in tumors and doxorubicin is released in the tumor by cleaving the acid labile linker (EMCH) in the low pH tumor environment. This carrier-linked prodrug has demonstrated enhanced anti-tumor activity with reduced toxicity in several murine models when compared with free doxorubicin. Patients with unresectable GBM who have failed prior surgery, radiation and chemotherapy with temozolomide regimens and bevacizumab have an extremely poor prognosis with progression-free survival (PFS) of around 8 weeks and median overall survival (OS) of approximately 8-16 weeks, depending on whether salvage therapy is administered. Recently, we have demonstrated in an orthotopic xenograft model of GBM in mice that ALDOXORUBICIN significantly retards the growth of the tumor and doubles the survival of animals when compared to treatment with either saline or doxorubicin. We have also shown that this molecule collects inside the tumor and not in normal brain parenchyma. Doxorubicin does not penetrate into either the tumor or the brain. Thus, ALDOXORUBICIN may be able to effectively treat patients with advanced GBM that have progressed after standard therapies.	

Name of Sponsor/Company: CytRx Corporation	
Protocol Number: ALDOXORUBICIN-P2-GBM-01	Phase of Development: 2

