
Study Design and Methodology: This is a phase 2 open-label, pilot study evaluating the preliminary efficacy and safety of ALDOXORUBICIN administered at either 350 mg/m² (260 mg/m² doxorubicin equivalent) or 250 mg/m² (185 mg/m² doxorubicin equivalent) intravenously on Day 1, every 21 days until evidence of tumor progression, unacceptable toxicity or withdrawal of consent. Subjects will be randomly assigned to either dose of ALDOXORUBICIN. G-CSF (Neupogen or Neulasta) should be administered as primary prophylaxis to all subjects according to the ASCO Guidelines (see Appendix E). Note: ALDOXORUBICIN, at higher doses, has been associated with >20% incidence of grade 3 or 4 neutropenia. Therefore, the administration of G-CSF should occur even during Cycle 1 for subjects receiving the 350 mg/m² dose of ALDOXORUBICIN.
 
Tumor response (complete response [CR], partial response [PR] and stable disease [SD]) will be monitored at Screening, then every 6 weeks (±5 days) using the RANO Working Group Criteria (see Appendix F), and treatment will continue every 21 days until tumor progression is observed, unacceptable toxicity occurs, or consent is withdrawn. Median PFS, PFS at 12 and 18 weeks, and 6 months, SD rate at 12 weeks, and OS will be monitored as other primary objectives. Subjects will visit the study site every 21 days for their IV infusions, at which time safety monitoring, including AEs, a directed physical examination, laboratory evaluations (serum chemistry and complete blood count [CBC]), vital signs, weight measurements, Karnofsky Performance Status (see Appendix B), documentation of corticosteroid usage and ECGs will be performed. All subjects will have blood drawn for serum electrolytes to evaluate the anion gap prior to each drug administration. Cardiac function will also be followed periodically using ECHOs.
	

Name of Sponsor/Company: CytRx Corporation	
Protocol Number: ALDOXORUBICIN-P2-GBM-01	Phase of Development: 2

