
 • PFS • OS • Objective tumor response (RANO Working Group Criteria [see Appendix F]) • PFS at 12 and 18 weeks and 6 months • SD rate at 12 weeks • Pseudo progression events on DSC-MRI in subjects who undergo additional MRI sequence evaluation • Karnofsky Performance Status (see Appendix B) • Corticosteroid usage 	

Name of Sponsor/Company: CytRx Corporation	
Protocol Number: ALDOXORUBICIN-P2-GBM-01	Phase of Development: 2

Safety: The following safety variables will be assessed over the course of the study:
 
 • AEs • Ability to remain on assigned treatment (tolerability) • Clinical and laboratory data including physical examinations, vital signs, weight, ECHO evaluations, ECG results and laboratory test results • Use of concomitant medications 	

Statistical Methods: In accordance with the intention-to-treat principle, all randomized subjects who enter active treatment and have had at least 1 dose of study medication and 1 post-dose efficacy measurement will be included in the primary statistical analyses.
 
Efficacy: Tumor response by MRI will be monitored every 6 weeks (± 5 days) until disease progression. For the estimation of PFS and OS a Kaplan-Meier analysis will be performed. The percentage of subjects with CRs or PRs, or SD will be evaluated every 6 weeks.
 
Safety: The safety data will be summarized for all subjects. Total number of AEs leading to withdrawal and abnormal laboratory tests will be evaluated. AEs, ability to remain on assigned treatment (tolerability), and abnormal findings on physical examinations, vital signs, weight, ECG results, ECHO, laboratory test results, and use of concomitant medications, will be assessed to characterize the safety profile of the treatment regimen. Descriptive evaluation denoting the changes from baseline to the final assessment visit with respect to key laboratory parameters and vital signs will also be provided.
	

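### The two laboratory statistics named for safety give no per-subject incidence by toxicity grade and do not show abnormal values that recover before the final visit

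*Combined protocol and SAP*

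**What the plan says.** The current text is the Amendment 4 synopsis, Statistical Methods, Safety. It makes three statements about laboratory data.

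1. A count: "Total number of AEs leading to withdrawal and abnormal laboratory tests will be evaluated". The grammar is loose, and the words on total number could govern only the adverse events. The natural reading is that both items are totals.
2. A change score: "Descriptive evaluation denoting the changes from baseline to the final assessment visit with respect to key laboratory parameters and vital signs".
3. A general statement that adverse events, laboratory results and other findings "will be assessed to characterize the safety profile of the treatment regimen". It names no statistic.

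The paragraph gives no per-subject rule, grade, worst value, shift table or split by dose. The secondary objective in the same synopsis is safety "assessed by the frequency and severity of adverse events (AEs), abnormal findings on physical examination, laboratory tests" and other measures.

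Footnote 5 of Appendix A requires a blood count every week in each cycle. After a drug-related or clinically significant toxicity, sites are to "retest frequently until stable or resolving and in accordance with GCP". This footnote text is printed with Amendment 1. The Amendment 4 schedule keeps the marker, but its footnotes are not in the public file. Treatment runs every 21 days with no fixed end. Up to 28 subjects are planned, 14 per dose level.

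The Amendment 4 Study Design section adds a note that the drug at higher doses "has been associated with >20% incidence of grade 3 or 4 neutropenia", and adds electrolytes before every dose to follow the anion gap. The Safety paragraph itself is the same as in Amendment 3.

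**The concern.** Safety is the secondary objective of a study that randomises between two dose levels. The usual question for laboratory toxicity is what share of subjects at each dose reached grade 3 or 4, and from what starting point. Neither named statistic answers it.

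A total of abnormal tests has no subject denominator. Retesting is triggered by an abnormal result, so one episode can be counted many times. The total also grows with the number of cycles received. If one dose level is treated for longer or retested more, its total rises even when the same number of subjects are affected.

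A change from baseline to the final visit ignores everything in between. The weekly blood counts and the pre-dose electrolytes are collected to detect values that move within and between cycles, yet this summary does not use them. A laboratory abnormality that has resolved by the final visit leaves no trace in it.

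**Working it through.** The documents give no design figure for laboratory safety, so there is nothing to reproduce. The check asks what each statistic can and cannot tell the reader.

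**Inputs from the documents:** 14 subjects per dose; 21-day cycles; weekly blood counts, so 3 scheduled per cycle; unscheduled repeats after toxicity; open-ended treatment.

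**Assumed inputs, for illustration only:** 2 or 6 cycles received; 3 of 14 subjects affected in every cycle; 1 or 3 low counts per affected cycle.

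**Step 1. Opportunity to be counted.** Scheduled counts per subject = 3 × cycles.
- 2 cycles: 6 per subject, 14 × 6 = 84 per arm.
- 6 cycles: 18 per subject, 14 × 18 = 252 per arm.

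**Step 2. Same incidence, different totals.** Incidence is 3/14 = 21.4% throughout. Total = affected subjects × cycles × low counts per cycle.

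| Cycles | Low counts per cycle | Total abnormal counts |
|---|---|---|
| 2 | 1 | 3 × 2 × 1 = 6 |
| 2 | 3 | 3 × 2 × 3 = 18 |
| 6 | 1 | 3 × 6 × 1 = 18 |
| 6 | 3 | 3 × 6 × 3 = 54 |

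The range is 54/6 = 9-fold at an unchanged incidence.

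**Step 3. Same total, different incidence.** With total T and at most c abnormal tests per subject, the number of affected subjects lies between T/c rounded up and the smaller of T and 14. Take c = 18 (6 cycles, scheduled tests only).
- T = 6: 1 to 6 subjects, 7.1% to 42.9%.
- T = 12: 1 to 12 subjects, 7.1% to 85.7%.

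So incidence cannot be recovered from the total.

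**Step 4. Final-visit change against worst change.** Let X0 be baseline and X1 to Xk the post-baseline neutrophil counts, with Xk the final one. The plan's change is Xk − X0. The worst change is min(X1, …, Xk) − X0. The minimum is never above Xk, so the plan's change never shows a larger fall than the worst change, and it shows the same fall only when the final value is the lowest. For the anion gap the argument is the same with the maximum. This needs no assumption about when the nadir falls or on which day the final sample is drawn.

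**Step 5. What the replacement would deliver.** Clopper-Pearson 95% intervals at 14 per dose:
- 3/14 = 21.4% (4.7% to 50.8%)
- 6/14 = 42.9% (17.7% to 71.1%)

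If the true rate is 20%, the chance of seeing at least one case is 1 − 0.8^14 = 0.956.

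**Step 6. Limit of the replacement.** Worst grade also rises with exposure. Assume, only to show the direction, a 20% chance per cycle, independent between cycles. The chance of ever reaching the grade is 1 − 0.8^2 = 0.36 over 2 cycles and 1 − 0.8^6 = 0.74 over 6. A Cycle 1 summary on the 3 scheduled weekly values gives every subject who completes that cycle the same opportunity.

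**The case against.** The strongest reply is that the incidence may be available by another route. The secondary objective covers the frequency and severity of adverse events. If every low count is reported as a graded event, the adverse-event table supplies most of what is asked for. The rules for reporting laboratory values as events are not in the public documents, so this can be neither confirmed nor ruled out. Those documents are synopses and schedules only, and a fuller statistical section may say more. Both points stand. They make this a gap in the stated laboratory summary, not a failure to collect the data.

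Four stronger readings are tempting and are not supported.

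- A reader might infer that the final blood count falls 3 weeks after the last dose and so always misses the nadir. That timing is in footnote 8, which concerns tumor response and is attached only to the MRI row. The end-of-study blood count has no stated day, and after early termination it could fall near a nadir. The documents do not say when the nadir occurs.
- A reader might treat the figure above 20% as a benchmark for the study. It is given as the reason for G-CSF in Cycle 1 at the higher dose. It is not an endpoint, and the documents do not say whether it arose with or without G-CSF.
- A reader might take the 9-fold range as an expected bias between arms. It follows from chosen inputs. The documents say only that retesting is frequent, and no difference between arms is known.
- A reader might expect a worst-grade table to remove all dependence on monitoring and exposure. It removes repeat counting within a subject, but longer treatment and more testing still raise it.

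**Conclusion.** The concern holds as a specification gap of moderate weight. On the natural reading of the Safety paragraph, the plan names two laboratory statistics. The first is not a function of how many subjects were affected: in the illustration, totals of 6 to 54 go with the same 21.4%, and a total of 6 fits 7.1% to 42.9%. The second uses a single post-baseline value that need not be the worst. If the count sentence is read the other way, the change score is the only laboratory statistic left, so no reading yields a per-subject incidence by grade.

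The retesting argument rests on footnote 5 as printed with Amendment 1 still applying under Amendment 4. The argument about the final-visit change does not depend on it. How much is lost in practice depends on the adverse-event reporting rules, which cannot be seen. In a descriptive pilot with 14 per dose, even the right statistic will be imprecise, but it can be interpreted and the total cannot.

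**What to change.** In Statistical Methods, Safety, replace the total of abnormal laboratory tests with the following, by dose level:

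- The number and percentage of subjects at each worst post-baseline CTCAE grade, using all scheduled and unscheduled values.
- A baseline-to-worst shift table for neutrophils, platelets and chemistries.
- The maximum on-treatment anion gap per subject, summarised descriptively.
- The worst-grade table repeated for Cycle 1, or per cycle on scheduled weekly values, so that differences in exposure and retesting do not drive the comparison.
- For adverse events leading to withdrawal, the number of subjects as well as the number of events.

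Keep the baseline-to-final change as a supplement. State whether graded laboratory abnormalities are also reported as adverse events, so that the two sets of tables can be read together. Show exact 95% intervals, so that the precision at 14 per dose is plain.

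The cost is a short addition to the text and a few standard tables from data already collected, with no added tests or visits. The estimates will remain wide.

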APPENDIX A: Schedule of Treatment and Evaluations

	Screening -21 Days	Cycle 1	All Other Cycles	Every 6 Weeks ± 5 Days from Cycle 1-Day 1	End of Study or Early Termination	Follow- up ¹²
Signed Informed Consent	X					
Review Inclusion/Exclusion		X				
Medical History ¹	X					
Physical Examination	X	X	X		X	
Height (cm)	X					
Weight (kg)	X	X	X			
BSA Calculation ²		X	X			
Vital Signs ³	X	X	X		X	
Karnofsky Performance Status	X	X	X		X	
MRI scan / Tumor Assessments	X ⁴			X ⁸	X ^{8,13}	
ECG	X	X ¹⁵	X ¹⁵		X ¹³	
ECHO (with ejection fraction)	X		X ¹¹		X ¹¹	
CBC w/differential & platelets ⁵	X	X ¹⁴	X		X	
Serum Chemistries ^{5,6}	X*	X ¹⁴	X		X	
Urinalysis ⁷	X				X	
Serum/Urine Pregnancy Test	X					
ALDOXORUBICIN Administration		X	X			
Concomitant Medications ⁹	X	X	X		X	
Adverse Events ¹⁰		X	X		X	
Telephone Follow-Up						X

NOTE: All assessments must be performed within 72 hours of each specified time parameter, except Cycle 1 (see Section 6 for details).

*Arterial blood gas test, if needed, to confirm acid levels.

CLINICAL PROTOCOL

TITLE: An Open-Label Pilot Phase 2 Study to Investigate the Preliminary Efficacy and Safety of Aldoxorubicin in Subjects with Unresectable Glioblastoma Multiforme Whose Tumors Have Progressed Following Prior Treatment with Surgery, Radiation and Temozolomide

PROTOCOL NUMBER: ALDOXORUBICIN-P2-GBM-01

STUDY DRUG: Aldoxorubicin

IND NUMBER: TBD

SPONSOR: CytRx Corporation
[name]
[name]
[contact]
[contact]

SAFETY [contact]

SAFETY [contact]

DATE OF PROTOCOL: August 9, 2013

CONFIDENTIAL

The information contained in this document is confidential and the proprietary property of CytRx Corporation. Any unauthorized use or disclosure of such information without the prior written authorization of CytRx Corporation is prohibited.

SYNOPSIS

Name of Sponsor/Company: CytRx Corporation	
Protocol Number: ALDOXORUBICIN-P2-GBM-01	Phase of Development: 2
Title of the Protocol: An Open-Label Pilot Phase 2 Study to Investigate the Preliminary Efficacy and Safety of Aldoxorubicin in Subjects with Unresectable Glioblastoma Multiforme Whose Tumors Have Progressed Following Prior Treatment with Surgery, Radiation and Temozolomide	
Primary Objectives: The primary objective of this study is to determine the preliminary efficacy of administration of ALDOXORUBICIN to subjects with unresectable glioblastoma multiforme (GBM) whose tumors have progressed following prior treatment with surgery, radiation and temozolomide.	
Secondary Objectives: The secondary objectives of this study are to evaluate the safety of ALDOXORUBICIN in this population assessed by the frequency and severity of adverse events (AEs), abnormal findings on physical examination, laboratory tests, vital signs, echocardiogram (ECHO) evaluations, electrocardiogram (ECG) results, and weight, and the change in performance status as measured by the Karnofsky Performance Scale.	
Study Rationale and Significance: ALDOXORUBICIN is a novel prodrug that binds covalently to albumin in the circulation. The drug is accumulated in tumors and doxorubicin is released in the tumor by cleaving the acid labile linker (EMCH) in the low pH tumor environment. This carrier-linked prodrug has demonstrated enhanced anti-tumor activity with reduced toxicity in several murine models when compared with free doxorubicin. Patients with unresectable GBM who have failed prior surgery, radiation and chemotherapy with temozolomide regimens and bevacizumab have an extremely poor prognosis with progression-free survival (PFS) of around 8 weeks and median overall survival (OS) of approximately 8-16 weeks, depending on whether salvage therapy is administered. Recently, we have demonstrated in an orthotopic xenograft model of GBM in mice that ALDOXORUBICIN significantly retards the growth of the tumor and doubles the survival of animals when compared to treatment with either saline or doxorubicin. We have also shown that this molecule collects inside the tumor and not in normal brain parenchyma. Doxorubicin does not penetrate into either the tumor or the brain. Thus, ALDOXORUBICIN may be able to effectively treat patients with advanced GBM that have progressed after standard therapies.	

Name of Sponsor/Company: CytRx Corporation	
Protocol Number: ALDOXORUBICIN-P2-GBM-01	Phase of Development: 2
Study Design and Methodology: This is a phase 2 open-label, pilot study evaluating the preliminary efficacy and safety of ALDOXORUBICIN administered at either 350 mg/m ² (260 mg/m ² doxorubicin equivalent) or 250 mg/m ² (185 mg/m ² doxorubicin equivalent) intravenously on Day 1, every 21 days until evidence of tumor progression, unacceptable toxicity or withdrawal of consent. Subjects will be randomly assigned to either dose of ALDOXORUBICIN. G-CSF (Neupogen or Neulasta) should be administered prophylactically according to the ASCO Guidelines (see Appendix E). Tumor response (complete, partial response [PR] and stable disease [SD]) will be monitored at Screening, then every 6 weeks using the Response Assessment in Neuro-Oncology (RANO) Working Group Criteria (see Appendix F), and treatment will continue every 21 days until tumor progression is observed, unacceptable toxicity occurs, or consent is withdrawn. Median PFS, PFS at 12 and 18 weeks, SD rate at 12 weeks, and OS will be monitored as other primary objectives. Subjects will visit the study site every 21 days for their IV infusions, at which time safety monitoring, including AEs, a directed physical examination, laboratory evaluations (serum chemistry, complete blood count [CBC], and urinalysis), vital signs, weight measurements, Karnofsky Performance Status (see Appendix B), corticosteroid usage and ECGs will be performed. Cardiac function will also be followed periodically using ECHOs.	

Name of Sponsor/Company: CytRx Corporation	
Protocol Number: ALDOXORUBICIN-P2-GBM-01	Phase of Development: 2
Study Population and Main Criteria for Inclusion/Exclusion:	
Inclusion Criteria:	
Subjects must meet the following criteria to be included in the study:	

 1. Age ≥ 18 years of age; male or female. 2. Histologically or cytologically confirmed unresectable GBM. Subjects with recurrent disease whose prior pathology demonstrated GBM will not need to be re-biopsied. Subjects with prior low-grade glioma or anaplastic glioma are eligible if histological assessment demonstrates transformation into GBM. 3. Cancer progression after treatment with the following: surgery, radiation therapy and temozolomide as first line treatment. 4. An interval of at least 4 weeks after last dose of radiation and temozolomide is required. 5. Stable or decreasing dose of corticosteroids for at least 7 days prior to enrollment. 6. Capable of providing informed consent and complying with trial procedures. 7. Karnofsky Performance Status (see Appendix B) ≥ 70. 8. Eastern Cooperative Oncology Group (ECOG) performance status 0-2. 9. Life expectancy ≥ 8 weeks. 10. Measurable tumor lesions according to RANO Working Group Criteria (see Appendix F). 11. Women must not be able to become pregnant (e.g. post-menopausal for at least 1 year, surgically sterile, or practicing adequate birth control methods) for the duration of the study. (Adequate contraception includes: oral contraception, implanted contraception, intrauterine device implanted for at least 3 months, or barrier method in conjunction with spermicide.) 12. Women of child bearing potential must have a negative serum or urine pregnancy test at the Screening Visit and be non-lactating. 13. Geographic accessibility to the site. 	
Exclusion Criteria:	
Subjects meeting the following criteria will not be enrolled:	

 1. Prior exposure to an anthracycline. 2. Prior treatment with bevacizumab or an experimental anti-angiogenic agent. 3. Palliative surgery and/or radiation treatment < 4 weeks prior to Randomization. 4. Exposure to any investigational agent within 30 days of Randomization. 5. History of other malignancies (except cured basal cell carcinoma, superficial bladder cancer or carcinoma in situ of the cervix) unless documented free of cancer for ≥ 3 years. 6. Laboratory values: Screening serum creatinine $> 1.5 \times$ upper limit of normal (ULN), alanine aminotransferase (ALT) $> 2.5 \times$ ULN, total bilirubin $> 1.5 \times$ ULN, absolute neutrophil count (ANC) $< 1,500/\text{mm}^3$, platelet concentration $< 100,000/\text{mm}^3$, absolute lymphocyte count $< 1000/\text{mm}^3$, hematocrit level $< 27\%$ for females or $< 30\%$ for males, serum albumin ≤ 2.5 g/dL. 7. Evidence of central nervous system (CNS) hemorrhage Common Terminology Criteria for Adverse Events (CTCAE) \geq grade 2 on baseline magnetic resonance imaging (MRI). 8. Clinically evident congestive heart failure (CHF) $>$ class II of the New York Heart Association (NYHA) guidelines (see Appendix D). 9. Current, serious, clinically significant cardiac arrhythmias, defined as the existence of an absolute arrhythmia or ventricular arrhythmias classified as Lown III, IV or V. 10. History or signs of active coronary artery disease with or without angina pectoris. 11. Serious myocardial dysfunction defined as ultrasound-determined absolute left ventricular ejection fraction (LVEF) $< 45\%$ of predicted institutional normal value. 	

Name of Sponsor/Company: CytRx Corporation	
Protocol Number: ALDOXORUBICIN-P2-GBM-01	Phase of Development: 2

12. Active, clinically significant serious infection requiring treatment with antibiotics, anti-virals, or anti-fungals.
 
13. History of HIV infection.
 
14. Major surgery within 4 weeks prior to Randomization.
 
15. Any condition that might interfere with the subject's participation in the study or in the evaluation of the study results.
 
16. Any condition that is unstable and could jeopardize the subject's participation in the study.
	
Number of Subjects: Up to 28 subjects will be enrolled (14 at each dose level) in 3-5 study centers in the US.	
Test Product, Dose and Mode of Administration: Lyophilized powder in vials that contain 200 mg of ALDOXORUBICIN reconstituted by adding a sterile solution of 50/50 ethanol:water, administration completed within 2 hours (of being reconstituted) as a 30 minute IV infusion in Lactated Ringer's solution. Total doses of either 350 mg/m ² (260 mg/m ² doxorubicin equivalent) or 250 mg/m ² (185 mg/m ² doxorubicin equivalents).	
Reference Therapy, Dose and Mode of Administration: None	
Criteria for Evaluation:	
Efficacy: The following efficacy variables will be evaluated as noted:	

 • PFS • OS • Objective tumor response (RANO Working Group Criteria [see Appendix F]) • PFS at 12 and 18 weeks • SD rate at 12 weeks • Karnofsky Performance Status (see Appendix B) • Corticosteroid usage 	
Safety: The following safety variables will be assessed over the course of the study:	

 • AEs • Ability to remain on assigned treatment (tolerability) • Clinical and laboratory data including physical examinations, vital signs, weight, ECHO evaluations, ECG results and laboratory test results • Use of concomitant medications 	

Name of Sponsor/Company: CytRx Corporation	
Protocol Number: ALDOXORUBICIN-P2-GBM-01	Phase of Development: 2
Statistical Methods: In accordance with the intention-to-treat principle, all randomized subjects who enter active treatment and have had at least 1 dose of study medication and 1 post-dose efficacy measurement will be included in the primary statistical analyses.	
Efficacy: Tumor response by MRI will be monitored every 6 weeks until disease progression. For the estimation of PFS and OS a Kaplan-Meier analysis will be performed. The percentage of subjects with complete or PRs, or SD will be evaluated every 6 weeks.	
Safety: The safety data will be summarized for all subjects. Total number of AEs leading to withdrawal and abnormal laboratory tests will be evaluated. AEs, ability to remain on assigned treatment (tolerability), and abnormal findings on physical examinations, vital signs, weight, ECG results, ECHO, laboratory test results, and use of concomitant medications, will be assessed to characterize the safety profile of the treatment regimen. Descriptive evaluation denoting the changes from baseline to the final assessment visit with respect to key laboratory parameters and vital signs will also be provided.	

